## **10 PROGRESS REPORTING**

### **10.1 Progress reports**

The CI or sponsor legal representative will submit, annually, starting at 12 months' post-date of favourable opinion, a progress report to the REC which issued favourable opinion, using the HRA progress report form for non-CTIMPs.

### **10.2 Declaration of conclusion**

The CI or sponsor legal representative will submit, within 90 days of study end, a declaration of study conclusion, to the REC which issued favourable opinion, using the HRA standard form.

### **10.3 Summary of final report**

The CI or sponsor legal representative will submit, within one year of study end, a summary of final report, to the REC which issued favourable opinion. The summary will be posted online by the HRA. It is intended that the final report will be presented at conference and published, but will primarily be used to obtain sufficient evidence for NICE and NHS England approval.

## **11 STATISTICS AND DATA ANALYSIS**

### **11.1 Sample size calculation**

If Alpha-Stim AID CES has a comparable effect to IAPT high intensity psychological therapy interventions in patients with a primary working diagnosis of GAD, it will achieve an effect size of 1.04 (95% CI 0.88 to 1.23) in an intention to treat sample of 4,183 participants with pre-treatment GAD-7 score of 14.06 (s.d. 5.11) and post treatment GAD-7 score of 8.10 (s.d. 6.37) (Richards and Borglin, 2011). Reliable improvement was obtained after IAPT treatment for generalised anxiety disorder in 54.7%, reliable improvement plus clinically significant change in 40.1% and recovery in 46.0%.

However, to make a meaningful economic impact on NHS care, then Alpha-Stim AID CES does not need to be as effective as IAPT high intensity psychological therapy interventions. In a previous randomised controlled trial (Barclay and Barclay 2014), Alpha Stim CES reduced the mean Hamilton Anxiety score from 29.5 to 13.4 while sham Alpha Stim CES reduced it from 27.6 to 20.0 over 5 weeks  $p=0.001$ ,  $d=0.94$ , with 83% patients showing a drop of 50% in HAM-A score.

A meta-analysis of 14 Alpha Stim CES randomised controlled trials estimates an average effect size of 0.60. On this basis reliable improvement may be seen in 33%, reliable improvement plus clinically significant change in 24% and recovery in 28% cases.

The cost of IAPT high intensity psychological therapy intervention is estimated to be £2,895.00 per participant and £2,914.00 if stepped care was involved (Radhakrishnan et al, 2013). On a cost offset basis if Alpha-Stim AID CES cost £465.00, then reliable improvement plus clinically significant change (which would not necessitate high intensity treatment) in only 20% would be clinically and cost effective.

Taking all data into account, 60 patients would be required to complete Alpha Stim AID CES treatment and all assessments. However, to allow for drop-out from assessments, drop-out from Alpha-Stim AID CES, and choice in relation to IAPT high intensity psychological therapy intervention ,120 patients will be recruited.

It is anticipated from a sample size of 120, then at least 40 (33%) would show reliable improvement, 29 (24%) plus clinically significant improvement, and 34 (28%) recovery at 6 months. Since a repeat course of Alpha-Stim from 6 to 12 weeks can result in further improvement in those who have made some improvement in symptoms, we estimate that a further 20 (17%) will make a reliable improvement in their symptoms. Therefore, it is anticipated that 60 (50%) will make a reliable improvement in their GAD-7 symptoms requiring no additional psychological treatment or a minimal psychological treatment intervention (in those with other symptoms or do not make a reliable improvement plus clinically significant change).

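### Do the underived 33%, 24% and 28% forecasts, and the 17% added to reach 50%, call for a change to section 11.1?

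*Combined protocol and SAP*

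**What the plan says.** Section 11.1 opens with a reference cohort treated with IAPT high intensity therapy. Its effect size is 1.04, with "pre-treatment GAD-7 score of 14.06 (s.d. 5.11) and post treatment GAD-7 score of 8.10 (s.d. 6.37". Reliable improvement was "obtained after IAPT treatment for generalised anxiety disorder in 54.7%, reliable improvement plus clinically significant change in 40.1% and recovery in 46.0" per cent. The section then turns to the device: "A meta-analysis of 14 Alpha Stim CES randomised controlled trials estimates an average effect size of 0.60". The next sentence gives the forecasts: "On this basis reliable improvement may be seen in 33%, reliable improvement plus clinically significant change in 24% and recovery in 28% cases". No formula links the 0.60 to them.

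The forecasts are then applied to 120 patients: "at least 40 (33%) would show reliable improvement, 29 (24%) plus clinically significant improvement, and 34 (28%) recovery at 6 months". A repeat course in weeks 6 to 12 is said to help those who have already improved somewhat, so "we estimate that a further 20 (17%) will make a reliable improvement in their symptoms". The section concludes: "Therefore, it is anticipated that 60 (50%) will make a reliable improvement in their GAD-7 symptoms".

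Three other places bear on the point. Section 3.4 defines reliable improvement as a GAD-7 fall of 5 or more from baseline to week 24. Sections 7.4 and 7.5 end all device treatment by week 12. Section 11.3 plans a mean and standard deviation at each visit and nothing further.

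**The concern.** Two things look wrong.

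The first is the conversion. All three forecasts are what one gets by multiplying the IAPT rates by 0.60. An effect size measures a shift in means in standard deviation units, and a responder rate does not scale in proportion to it. The two effect sizes may also differ in kind. The 1.04 is a before-after change in one cohort. The 0.60 comes from randomised trials and its type is not stated. If it is a contrast with control, it cannot yield a single-arm response rate without the change in the control arm.

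The second is timing. A rate at 6 months should already include any gain from a course that ended at week 12, yet 17% is added on top of it. The 17% has no citation and the 50% has no date.

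If the sample size or a success criterion rested on these rates, the study could be the wrong size or be judged against the wrong benchmark. The 24% also stands near the 20% rate that section 11.1 calls sufficient on a cost-offset basis.

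**Working it through.** **Inputs from section 11.1.** IAPT rates 54.7, 40.1 and 46.0%; IAPT effect size 1.04; GAD-7 14.06 (SD 5.11) before and 8.10 (SD 6.37) after; CES effect size 0.60; 120 patients recruited. The correlation between the two GAD-7 scores is not given; 0 to 0.7 is assumed.

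**1. Reproducing the forecasts.**
- 0.60 × 54.7 = 32.8; 0.60 × 40.1 = 24.1; 0.60 × 46.0 = 27.6. These round to 33, 24 and 28.
- Rescaling by the ratio of effect sizes, 0.60/1.04 = 0.577, gives 31.6, 23.1 and 26.5, which round to 32, 23 and 27 and match none.
- The multipliers that round to 33, 24 and 28 run over 0.594–0.612, 0.586–0.611 and 0.598–0.620. The overlap is 0.598–0.611, so 0.60 is a very likely rule, though an inferred one.

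**2. Is the rule sound?** No.
- At the IAPT effect of 1.04 it returns 1.04 × 54.7 = 56.9%, not the 54.7% seen at that effect.
- At zero effect it returns 0%. Take change as normal with SD = √(5.11² + 6.37² − 2ρ × 5.11 × 6.37), which is 8.17 at ρ = 0 and 4.60 at ρ = 0.7. Then 27% and 14% of patients fall by 5 or more with no mean change.
- The 1.04 is a pre-post figure: (14.06 − 8.10) / ((5.11 + 6.37)/2) = 5.96/5.74 = 1.04.

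**3. Are the printed rates wrong in size?** Suppose, as an assumption, that 0.60 is also a pre-post effect.
- Mean fall 0.60 × 5.11 = 3.07 or 0.60 × 5.74 = 3.44. The normal model gives P(fall ≥ 5) = 34–42% over ρ = 0.7 to 0.
- As a check, the same model at the cited fall of 5.96 gives 55–58%, against the cited 54.7%.
- That model ignores the entry criterion in section 6.1 (GAD-7 of 10 or more). Restricting the baseline to 9.5 or above on the continuous scale, with an unrestricted mean fall of 3.07 and post-treatment cuts at 9.5 and 7.5, gives:

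| Outcome | Printed | Model, ρ = 0.7 to 0 |
|---|---|---|
| Reliable improvement | 33% | 35–48% |
| Reliable improvement plus clinically significant change | 24% | 22–35% |
| Recovery | 28% | 19–29% |

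The first printed rate lies just below its range and the other two lie inside theirs. The ranges illustrate size only; they depend on an assumed correlation and on an assumed reading of the 0.60.

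**4. The counts.** 120 × 0.33 = 39.6, 120 × 0.24 = 28.8 and 120 × 0.28 = 33.6, giving 40, 29 and 34. 20/120 = 16.7%. (40 + 20)/120 = 50%. The printed sums are correct. The added 20 are 20/(120 − 40) = 25% of those not already counted as reliably improved.

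**5. What uses these numbers?** Section 11.1 arrives at 60 completers by taking all the data into account, with no alpha, power or precision target, and moves to 120 to allow for drop-out and patient choice. Neither number is computed from 33, 24, 28, 17 or 50%. Section 11.3 contains no test or comparison that refers to them.

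**The case for a change.** The case for a change is that these are the only expected rates stated for the device, in a study meant chiefly to inform NICE and NHS England. The 50% is tied to patients needing little or no further psychological treatment, which is an economic claim. The 24% is not clearly separated from 20% by the data this study will yield: at 29/120 the exact 95% interval is 16.8–32.8%. Rewording would cost no patients, visits or analyses.

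Part of this stands. The derivation is undisclosed, the type of the 0.60 is not given, the 17% is uncited, and the 6-month label sits badly beside what appears to be a first-course figure. Someone quoting these forecasts elsewhere should know that.

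The rest is weaker. Section 11.1 gives a floor (at least 40), an increment (a further 20) and a stated total (60), so 50% is its conclusion. The increment has a reason attached and is openly labelled an estimate. Limiting it to reliable improvement is coherent, because the closing sentence allows for patients who do not also reach clinically significant change. The 20% is a cost-offset argument, not a test threshold; the section's own costs break even at 465/2,895 = 16.1%. Asking for precision around 20% would add a requirement unrelated to how the forecasts were obtained. Deleting the forecasts would remove the only expectations stated in advance.

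**Conclusion.** No change follows. Section 11.1 leaves its forecasts without a derivation, probably used an unsound shortcut, and labels one time point loosely. These are faults of background explanation. Re-deriving, relabelling or deleting the figures would leave the 60 and 120, the outcome definitions, the visits and the planned summaries as they are, and no result or conclusion would differ.

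The size of any error is not established, nor its direction. On a pre-post reading of 0.60 the printed 33% is slightly low and 24% and 28% are within range. On a between-group reading the documents do not give enough to compute a rate. The conclusion rests on the forecasts staying descriptive, as section 11.3 leaves them. The multiplication by 0.60 is inferred from a three-out-of-three match, and the model ranges rest on an assumed correlation of 0 to 0.7 and normal scores. An analyst reporting week-24 rates under section 3.4 would count every patient at week 24, including those who took the repeat course, so the ambiguity between 33% and 50% does not reach the results.

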## **8.2 End of study provision**

The device is marketed and sold in the UK by the sponsor legal representative, and are available from private purchase at a cost of £499.00. Participants will be fully informed that participation in the study will result in a maximum of 12 weeks of Alpha-Stim AID device treatment, after which time point the device must be returned to the research nurse. Participants will not be encouraged to purchase a device, but will be advised by the research nurse if an interest is expressed. Participants will not receive a discount on the purchase of a device.

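### The 20% cost-offset figure in section 11.1 counts every raw improver as a therapy course saved; it should be net of improvement expected without the device, and the 60 completers need a stated basis

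*Combined protocol and SAP*

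**What the plan says.** Section 11.1 (Sample size calculation) sets the cost of the device against the cost of high intensity therapy. The therapy is "estimated to be £2,895.00 per participant and £2,914.00 if stepped care was involved". The comparison is conditional: "if Alpha-Stim AID CES cost £465.00", then reliable improvement plus clinically significant change "in only 20% would be clinically and cost effective". The reason given is that such an outcome is one "which would not necessitate high intensity treatment", so each improver offsets a whole course.

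The same section expects this outcome in 24%, which for 120 participants it gives as "29 (24%) plus clinically significant improvement", counted at 6 months. On size it says: "Taking all data into account, 60 patients would be required to complete Alpha Stim AID CES treatment and all assessments". It then doubles this to 120 recruited, to allow for drop-out and for choice about therapy.

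Section 8.2 gives a second price: the device is "available from private purchase at a cost of £499.00". The Study Summary and section 4 describe a study of one device with no comparison group. Section 11.3 plans means and standard deviations at each visit.

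**The concern.** A cost offset is earned only by therapy that the device makes unnecessary. A participant who would have improved anyway, or who improved because high intensity therapy had already begun, saves nothing that can be credited to the device. The 20% sentence makes no such deduction, and a single-arm study cannot make it from its own data.

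This matters because sections 2 and 10.3 say the results are meant chiefly as evidence for NICE and NHS England. The 20% is the only response rate that the plan ties to cost effectiveness. A reader who sets a raw rate above 20% against that sentence could conclude that the device pays for itself when no saving is attributable to it. Beside it, the number of completers is given without a criterion, so the reader cannot tell how precisely the rate will be known.

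**Working it through.** **Inputs.** Device cost £465 (section 11.1) or £499 (section 8.2). Therapy cost £2,895, or £2,914 with stepped care (11.1). Expected rate 24% (11.1). Share who would improve without the device, b: not in the documents, so shown as a range.

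**1. Can 20% be reproduced?** Gross break-even = device cost / therapy cost.

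- 465/2,895 = 16.06%; 465/2,914 = 15.96%
- 499/2,895 = 17.24%; 499/2,914 = 17.12%

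None gives 20%. For 20% to be break-even, the device would have to cost 0.20 × 2,895 = £579, or the therapy 465/0.20 = £2,325. Neither figure is in the documents. At a 20% rate the gross saving per patient is 579 − 465 = £114, or 579 − 499 = £80. So 20% lies above break-even by 20 − 16.06 = 3.9 points, or 2.8 points at £499, and no reason for that margin is given.

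**2. Net of improvement without the device.** With raw rate p, saving per patient = (p − b) × 2,895 − 465. Setting this to zero gives p = b + 16.06% (b + 17.24% at £499).

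| b (assumed) | raw rate needed, £465 | raw rate needed, £499 |
|---|---|---|
| 0% | 16.1% | 17.2% |
| 5% | 21.1% | 22.2% |
| 8% | 24.1% | 25.2% |
| 10% | 26.1% | 27.2% |

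The 20% stops being enough once b exceeds 3.9% (2.8% at £499). The expected 24%, read as a gross rate, stops once b exceeds 24 − 16.06 = 7.9% (6.8% at £499). The formula still credits each net improver with a full course avoided. Anyone who has begun therapy by week 24 saves less, which would push the required rate up.

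**3. Is b likely to be zero?** The documents suggest not, though they do not size it. In the randomised trial cited in section 11.1, Hamilton Anxiety fell 27.6 − 20.0 = 7.6 points on sham, against 29.5 − 13.4 = 16.1 on active treatment. No sham responder rate is given, so this cannot be converted to b. Section 7 allows high intensity therapy to begin after a minimum wait of 6 to 8 weeks. Section 7.4 expects the optional second device course to coincide with it. The 24% is counted at 6 months.

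**4. What 60 and 120 deliver.** Half-width of a 95% interval at 24%, by 1.96 × √(0.24 × 0.76/n): 10.8 points at n = 60 and 7.6 at n = 120. Exact (Clopper-Pearson) 95% intervals for counts nearest 24%:

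- 14/60: 13.4% to 36.0%, containing 16.1%, 17.2% and 20%
- 29/120: 16.8% to 32.8%, excluding 16.1% but containing 17.2% and 20%

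Set against break-even plus b, the lower limit from 14/60 falls short even at b = 0. The lower limit from 29/120 clears the £465 break-even only while b is below 16.82 − 16.06 = 0.8 points.

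**5. Where 60 comes from.** Section 11.1 gives no hypothesis, significance level, power, precision target or formula. The 120 equals 60/(1 − 0.50), but no rate of loss is stated.

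For illustration only, take an exact one-sided 2.5% test and a true rate of 24%. Against 16.06% the cut-offs are 16/60 and 28/120, with power 36% and 60%. Against 20% they are 19/60 and 34/120, with power 11% and 16%.

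**The case against.** Several replies have force.

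*The 20% is not wrong arithmetic.* A reader might infer that a break-even of 16.1% refutes it. It does not. The sentence says 20% would be sufficient and never calls it a break-even; on gross figures it is sufficient. This stands in full.

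*The 20% is not a decision rule.* No section says the observed rate will be compared with it. Section 3.5 assigns the cost-effectiveness objective to the CSRI, EQ-5D-5L and WASA. This stands too: the problem is an unsound justification that invites misuse, not a planned test that would go wrong.

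*The 24% may not be a gross rate.* It matches 0.60 × 40.1% = 24.1%, that is, an effect size from randomised trials applied to an uncontrolled therapy rate. Whether that is gross, net or mixed is unclear, and deducting all of b may double-count. The limit of about 8% is therefore conditional. The rate the study observes will be gross in any case.

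*The price is an assumption.* £465 is conditional and £499 is a private retail price, so the two need not conflict. Sections 8.3 and 11.1 also have 60 devices for 120 participants. If each device served two people, break-even would be 232.50/2,895 = 8.0%, and 20% would hold up to b of about 12%. The figures above keep the plan's own basis of one £465 cost per participant.

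*Power is imported.* A reader might infer that 60 is too few to separate 24% from the threshold. The plan never says that 60 was chosen for that purpose and proposes no test, so the power figures cannot count as a failure of the plan. What remains is that 60 has no stated basis.

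**Conclusion.** The point holds as a fault in reasoning. Section 11.1 treats a raw single-arm improvement rate as therapy saved by the device, so a raw rate of 20% would not by itself show cost effectiveness. At £465 per participant and £2,895 per course avoided, 20% is enough only if no more than about 4% would improve without the device; for 24%, if gross, the limit is about 8%. These limits rest on the plan's prices, on a full course avoided for each net improver, and on values of b that the documents do not supply.

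The choice of 20% over 16.1% is unexplained but not an error, and 60 is underived but not shown to be inadequate for any purpose the plan declares. The supportable statement on size is the precision in step 4.

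**What to change.** Reword section 11.1:

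- State the gross break-even as 16.1% at £465, with 17.2% at £499 as sensitivity, and explain the 20% or remove it.
- Say that break-even is the increment over improvement expected without the device.
- Compare the lower 95% limit of the observed rate with break-even plus a stated range of b, and not with 16.1% or 20% alone. Setting a raw rate against a net threshold would repeat the fault.
- Replace the claim that 60 are required with the precision delivered at a rate of 24%: about ±10.8 points at 60 completers and ±7.6 at 120. If power is mentioned at all, label it illustrative.

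This needs no more patients, visits or data. The price is a more modest cost-effectiveness claim, and the sponsor must choose and justify a range for b from a source outside the present documents.

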### **11.2 Planned recruitment rate**

According to IAPT service data, 11.7% cases referred to IAPT meet criteria to establish a primary working diagnosis GAD. Of these 39.1% make no clinical improvement and are still clinical cases with a primary working diagnosis of GAD upon completion of low intensity psychological therapy intervention (Richards and Borglin, 2011). On this basis 4.6% of all referrals to the three teams within the single IAPT service should be eligible so a conservative estimate is that 2.0% of all referrals may be recruited to this study, allowing for exclusions and 50% consent to participation. The IAPT service receives 11,000 referrals per year each leading to 440 potential participants.

It is planned that recruitment will be complete within 6 months.

### **11.3 Statistical analysis plan**

Mean and standard deviation scores will be reported for each visit time-point. The statistician who will deliver the analysis is:

[name]., PStat  
Professor – Psychometrics & Statistics  
Accredited Professional Statistician - American Statistical Association  
Director – Initiative for Interdisciplinary Research Design & Analysis (IIRDA)  
Texas State University  
[name]  
Email: [[contact]](mailto:[contact])

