## **2 RATIONALE**

The purpose of this study is not demonstrate clinical effectiveness of Alpha-Stim AID CES – the device has a CE marking and there are sufficient clinical trials to demonstrate effectiveness. The purpose of this study is to address the paucity of data on the clinical effectiveness and cost effectiveness in an NHS setting. For Alpha-Stim AID CES treatment to be available as standard care within the IAPT service, the treatment must be appraised by NICE, which will require evidence of clinical effectiveness in the NHS, and an assessment of the economic impact.

The study will also be published to demonstrate to an international audience of how Alpha-Stim AID CES can complement psychological therapy intervention within a care pathway, which may then be commissioned in other health and social care systems. However, the study is primarily designed to obtain sufficient evidence for NICE and NHS England.

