### 3 OBJECTIVES AND OUTCOME MEASURES

#### 3.1 Primary objective

The primary objective of this study is to evaluate the clinical effectiveness of treatment with Alpha-Stim AID cranial electrotherapy stimulations (CES) for participants with a primary working diagnosis of generalised anxiety disorder (GAD), as defined by the NHS IAPT service in terms of reliable improvement, clinically significant improvement, and recovery, from baseline to week 24, following previous treatment with low intensity psychological therapy intervention.

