#### 3.4 Primary outcome measures

The primary objective will be measured using GAD-7 scores, which is a participant-reported screening tool and severity measure for generalised anxiety disorder (GAD).

- The outcome measure for **reliable improvement of GAD** is defined as participants who reach a score reduction of 5 or more from baseline to week 24. Such a reduction amounts to a clinically important change. Some reliable improvement is defined as participants who reach a score reduction of 1 – 4 from baseline to week 24. No reliable improvement is defined as participants who reach no score reduction from baseline to week 24.
- The outcome measure for **clinically significant improvement of GAD** is defined as participants with a score of 10 or more at baseline, who reach 9 or fewer by week 24.
- The outcome measure for **recovery of GAD** is defined as participants with a score of 10 or more at baseline, who reach 7 or fewer by week 24.

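### The primary outcome is three week-24 GAD-7 responder classifications, but the only planned analysis is visit means and SDs, with no denominator, interval or missing-score rule

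*Combined protocol and SAP*

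**What the plan says.** Section 3.1 sets the primary objective "in terms of reliable improvement, clinically significant improvement, and recovery, from baseline to week 24". Section 3.4 turns this into three yes/no classifications of each person on the GAD-7:

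- reliable improvement: "participants who reach a score reduction of 5 or more from baseline to week 24";
- clinically significant improvement: "participants with a score of 10 or more at baseline, who reach 9 or fewer by week 24";
- recovery: the same baseline condition, with a score of 7 or fewer.

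Apart from the statistician's details, section 11.3 is one sentence: "Mean and standard deviation scores will be reported for each visit time-point".

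Section 11.1 is written largely in responder percentages, on two bases. It asks for a completer number, "60 patients would be required to complete Alpha Stim AID CES treatment and all assessments", and doubles it to 120 to cover loss from assessments, loss from the device and choice about high intensity therapy. It then forecasts out of everyone recruited: "from a sample size of 120, then at least 40 (33%) would show reliable improvement, 29 (24%) plus clinically significant improvement", with 34 (28%) recovering at 6 months. It also uses a composite, reliable improvement together with clinically significant change, in a cost-offset argument: "reliable improvement plus clinically significant change (which would not necessitate high intensity treatment) in only 20% would be clinically and cost effective". Section 3.4 does not list that composite.

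On incomplete data, section 7.7 asks for best efforts to regain contact. Section 7.8 keeps data collected before withdrawal unless the participant asks for removal. Neither says how a missing week-24 score is counted.

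**The concern.** Followed as written, section 11.3 does not answer the primary objective. A visit mean describes a group on one occasion, whereas reliable improvement depends on each person's change and the other two outcomes depend on how many people lie below a cut-off. The proportions could be worked out from the scores collected, but nothing fixes in advance who is counted, how a missing score is classified or how uncertainty is shown.

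This matters because section 2 ties the study to a NICE appraisal, "which will require evidence of clinical effectiveness in the NHS, and an assessment of the economic impact", and section 11.1 rests the clinical and cost-offset case mainly on responder percentages. The study has no comparator, so the reported percentage and its precision are the result. Recruiting twice the number needed to complete shows that substantial loss is allowed for. A denominator chosen after the data are seen could then change the headline materially.

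**Working it through.** **1. Reproduce the plan's forecast.** Inputs, all from section 11.1: responder rates after IAPT treatment of 54.7% (reliable improvement), 40.1% (composite) and 46.0% (recovery); an average CES effect size of 0.60; 120 recruited.

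- 0.60 × 54.7 = 32.8%; 0.60 × 40.1 = 24.1%; 0.60 × 46.0 = 27.6%. These round to the stated 33%, 24% and 28%.
- 120 × 0.33 = 39.6; 120 × 0.24 = 28.8; 120 × 0.28 = 33.6. These round to the stated 40, 29 and 34.

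The forecast reproduces, and its basis is everyone recruited. The 60 completers cannot be derived, because no alpha or power is stated. The step from 60 to 120 matches 60 / (1 − 0.5) = 120, so it implies an allowance of half.

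**2. Do visit means and SDs fix the proportions?** A constructed example with 120 people:

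- Baseline: 60 score 12 and 60 score 18 (mean 15.0, SD 3.01). Week 24: 60 score 6 and 60 score 12 (mean 9.0, SD 3.01).
- If those at 12 go to 6 and those at 18 go to 12, everyone falls by 6: reliable improvement is 120/120.
- If those at 12 stay at 12 and those at 18 go to 6, reliable improvement is 60/120. Both visit means and SDs are unchanged.
- Replace the week-24 scores by 15 at 3, 90 at 9 and 15 at 15. Mean and SD are still 9.0 and 3.01, but recovery goes from 60/120 to 15/120 and clinically significant improvement from 60/120 to 105/120.

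So the planned summaries do not determine any of the three outcomes.

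**3. Precision at the forecast counts.** Exact (Clopper-Pearson) 95% limits for x of n are the 2.5% point of Beta(x, n − x + 1) and the 97.5% point of Beta(x + 1, n − x).

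| Outcome | Count | % | 95% CI |
|---|---|---|---|
| Reliable improvement | 40/120 | 33.3 | 25.0 to 42.5 |
| Recovery | 34/120 | 28.3 | 20.5 to 37.3 |
| Composite (section 11.1 only) | 29/120 | 24.2 | 16.8 to 32.8 |

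The composite's interval includes the illustrative 20% cost-offset figure. Section 11.1 gives no forecast for clinically significant improvement on its own.

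**4. Effect of the denominator.** The documents give no week-24 missing rate, so a range is shown. Assumption: one third of those observed show reliable improvement, as in the forecast.

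| Missing | Observed cases | Missing counted as not improved |
|---|---|---|
| 0 | 40/120 = 33.3% (25.0 to 42.5) | 40/120 = 33.3% (25.0 to 42.5) |
| 30 | 30/90 = 33.3% (23.7 to 44.1) | 30/120 = 25.0% (17.6 to 33.7) |
| 60 | 20/60 = 33.3% (21.7 to 46.7) | 20/120 = 16.7% (10.5 to 24.6) |

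Sixty missing is the upper case implied by 120 against 60. The allowance in section 11.1 also covers stopping the device and therapy choice, so fewer week-24 scores may be lost.

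**The case against.** The strongest reply is that the gap is one of drafting. Section 3.4 gives exact cut-offs, individual scores are collected at every visit, section 11.3 does not say that nothing else will be reported, and forecasts expressed as counts of 120 suggest that counts will be given. Section 11.1 also uses effect sizes and GAD-7 means and SDs, which visit summaries do serve, and section 2 says that the purpose is not to demonstrate the device's effectiveness. All of this is accurate. It shows that the proportions can be calculated, not that a population, an interval or a missing-score rule has been chosen. The mentions of intention to treat and of a 95% interval in section 11.1 belong to a cited cohort. Section 2 itself also asks for effectiveness evidence in the NHS.

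Three stronger readings are tempting, and the documents do not support them.

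- A reader might treat 20% as a success threshold that the study is likely to miss. It is a cost-offset illustration attached to a composite that is not a listed outcome. Section 11.1 also expects a further 20 (17%) reliable improvers after a second course, 60 (50%) in all, and gives no updated composite figure.
- A reader might infer that changing the denominator would lift the composite's interval wholly above 20%. Keeping all 29 responders while the denominator shrinks requires every missing person to be a non-responder, and nothing in the documents says so.
- A reader might see a conflict of timing in section 3.4, where one outcome runs to week 24 and the others are reached by week 24. Section 3.1 applies baseline to week 24 to all three, and section 11.1 places recovery at 6 months. The wording needs tidying, no more.

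**Conclusion.** The point stands and should be corrected before analysis. The named analysis cannot produce the primary outcome, and the denominator, interval and missing-score rule are all unset. The outcome definitions themselves are present; the gap is in the analysis plan.

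The size depends on losses. With none missing, the denominator makes no difference and the missing piece is the interval, roughly 8 to 9 percentage points either side at the forecast counts. With 60 missing and one third of those observed responding, reliable improvement is 33.3% or 16.7% depending on a choice the plan leaves open. Both the 60 and the constant one-third rate are assumptions. That the means and SDs are insufficient rests on no assumption.

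**What to change.** In section 11.3:

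- Make the primary analysis the number and percentage, with exact 95% interval, of participants meeting each section 3.4 outcome on the week-24 score.
- Use as denominator all participants confirmed eligible at baseline. Section 7.3 requires a GAD-7 of 10 or more at that visit, so one denominator serves all three outcomes. Exclude only those who ask for their data to be removed (section 7.8), and state how many.
- Name one missing-score rule in advance. Counting a missing week-24 score as not improved is one defensible choice and keeps the out-of-120 basis of the forecast. Its downside is a lower headline, which could be much lower if losses approach 60.
- Report alongside it the observed-case proportion and a proportion from multiple imputation of the week-24 score using earlier GAD-7 scores.
- Keep the visit means and SDs as supporting description.

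In section 3.4, list the composite (a fall of 5 or more and a score of 9 or fewer) as a descriptive outcome, since section 11.1 relies on it, and state that all outcomes are read at week 24.

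The cost is wording in two sections and a few tables. The GAD-7 is already scheduled at all six visits, so no new data are needed.
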